5.3.2 Exclusion Criteria

Subjects are not eligible for this trial if they fulfill any of the following exclusion criteria:

1. Participation in another interventional clinical trial within the past 30 days (participation in observational studies are permitted)
2. Concurrent treatment with a nonpermitted drug
3. Prior therapy with any antibody/drug targeting T-cell coregulatory proteins (immune checkpoints) such as anti-PD-1, anti-PD-L1, or anticytotoxic T-lymphocyte antigen-4 (CTLA-4) antibody; for Part B, the Investigator must consult with the Medical Monitor and consider other co-regulatory targets such as 4-1BB
4. Concurrent anticancer treatment (for example, cytoreductive therapy, radiotherapy [with the exception of palliative bone-directed radiotherapy, or radiotherapy administered on non-target superficial lesions], immune therapy, or cytokine therapy except for erythropoietin). Radiotherapy administered to superficial lesions is not allowed if such lesions are considered target lesions in the efficacy evaluation or may influence the efficacy evaluation of the investigational agent
5. Major surgery for any reason, except diagnostic biopsy, within 4 weeks and/or if the subject has not fully recovered from the surgery within 4 weeks
6. Concurrent systemic therapy with steroids or other immunosuppressive agents, or use of any investigational drug within 28 days before the start of trial treatment. Short-term administration of systemic steroids (that is, for allergic reactions or the management of irAEs) is allowed while on study. Also, subjects requiring hormone replacement with corticosteroids for adrenal insufficiency are eligible if the steroids are administered only for the purpose of hormonal replacement and at doses ≤ 10 mg or equivalent prednisone per day. Note: Subjects receiving bisphosphonate or denosumab are eligible
7. Subjects with active central nervous system (CNS) metastases are excluded. Subjects with a history of treated CNS metastases (by surgery or radiation therapy) are not eligible unless they have fully recovered from treatment, demonstrated no progression for at least 2 months, and do not require continued steroid therapy
8. For Part A: Previous malignant disease (other than MCC) within the last 5 years with the exception of basal or squamous cell carcinoma of the skin or cervical carcinoma in situ

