| RECIST 1.1 | Response Evaluation Criteria in Solid Tumors version 1.1 |
| SAE | Serious adverse event |
| SAP | Statistical Analysis Plan |
| SD | Stable disease |
| SLD | Sum of target lesion diameters |
| SMC | Safety Monitoring Committee |
| TEAE | Treatment-emergent adverse event |
| TTP | Time to progression |
| ULN | Upper limit of normal |
| US | United States |
| WBC | White blood cell |

4 Modification History

| Unique Identifier for SAP Version | Date of SAP Version | Author | Changes from the Previous Version |
|-----------------------------------|---------------------|--------|---|
| 1.0 | 18 March 2016 | PPD | NA. The first version |
| 2.0 | 20 October 2016 | PPD | 
 1. Updated in accordance with Protocol v10 (20-Oct-2016) 2. Modified subgroup analysis sets in Section 10 to match Part A SAP 3. Updated irAE definition in accordance with Part A; added Appendix II 4. Minor editorial updates |
| 3.0 | 16 November 2017 | PPD | 
 1. Updated in accordance with Protocol v11 (17-May-2017) 2. Changed CRO name from 'PPD' to 'PPD' 3. Updated language to use 'study' instead of 'trial' to be consistent with current Harmonized SAP (except in text copied directly from Protocol) 4. Updated Per Protocol Analysis Set definition to match current list of Clinically Important PDs 5. Removed references to replicate ECG measurements 6. Australia and/or Latin America will now be included as additional pooled geographical regions if there are ≥ 10 subjects in FAS (instead of $> 10\%$ of FAS) 7. Updated subgroup categories of time from initial diagnosis to study entry to: ≤ 3 months, > 3 months and ≤ 1 year, > 1 year 8. Added subgroup for time from occurrence of metastatic disease to study entry 9. Updated definition of on-treatment period to end at start of new anti-cancer drug therapy (instead of any anti-cancer therapy), when applicable 10. Added specifications for handling summary statistics over time 11. Removed ECG assessments from visit windowing 12. Re-assigned AVISITN values in visit windowing 13. Changed 'randomized treatment' to 'study treatment' as this is a non-randomized study 14. Removed from AE data imputation rules: 'If stop date of AE is after date of cut-off outcome of AE is ongoing at cut-off.' 15. Added date imputation rule for subsequent anti-cancer therapy 16. Updated Geographic Region values and added EEA in Demographics section |

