8.3 Final Analysis

All planned analyses outlined in this SAP will be performed for the primary analysis. A partial database lock will be performed for the interim and primary analyses. The full DB lock will take place 5 years after the last subject receives the last dose of avelumab, or when the last subject dies, whichever occurs first.

In addition, no database can be locked until this SAP has been approved.

Subjects follow-up for progression and survival will continue until 5 years after the last subject receives the last dose of avelumab, or when the last subject dies, whichever occurs first. Under some circumstances, subjects may not be followed for 5 years for survival in this study, for example, subjects may be offered to enroll into a rollover study, or the Sponsor may terminate the study early.

9 Changes to the Planned Analyses in the Clinical Trial Protocol

The statistical methods as described in the protocol for Part B of this study were adopted.

10 Analysis Sets

Screening Analysis Set

The screening analysis set includes all subjects who signed the informed consent.

Full Analysis Set / Safety Analysis Set

Full analysis set (FAS) / Safety analysis set will include all subjects who received at least one dose of study drug.

Per Protocol Analysis Set

The Per-Protocol (PP) analysis set is a subset of the FAS and includes all FAS subjects who meet all of the following criteria that could impact the key objectives of the study:

- Measurable disease per RECIST 1.1 and IERC assessment
- Distant metastatic disease
- No prior anti-cancer therapy for metastatic disease
- No prior therapy with any antibody/drug targeting T-cell coregulatory proteins such as anti-PD-1, CCI, or anticytotoxic T-lymphocyte antigen-4 (CTLA-4) antibody
- Histologically proven MCC with confirmation of the diagnosis by immuno-histochemistry detection of CK20 (or other appropriate cytokeratin expression such as pancytokeratin, AE1/AE3, or Cam5.2) according to the assessment documented in the “Disease History” eCRF page.
- No active central nervous system (CNS) metastases; subjects with a history of treated CNS metastases (by surgery or radiation therapy) must have fully recovered from treatment, demonstrated no progression for at least 2 months, and not require continued steroid therapy.

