13.3.2 Prior Anti-Cancer Therapies

The prior anti-cancer therapies are collected under the “Prior Anti-Cancer Drug Therapies Details”, “Prior Anti-Cancer Radiotherapy Details” and “Prior Anti-Cancer Surgeries Details” eCRF pages.

The number of subjects in each of the following anti-cancer therapy categories will be tabulated:

- Subjects with at least one type of prior anti-cancer treatment
- Subjects with at least one prior anti-cancer drug therapy
- Subjects with at least one prior anti-cancer radiotherapy
- Subjects with at least one prior anti-cancer surgery

Prior systemic anti-cancer drug therapy will be summarized as follows:

- Number of prior systemic anti-cancer therapy: missing / 0 / 1 / 2 / >2
- Duration of prior chemotherapy
- Type of prior anti-cancer therapy: Chemotherapy / Hormonal therapy / Antibody therapy / Kinase inhibitors / Vaccines / Other
- Number of prior systemic anti-cancer therapies by disease setting: Neo-Adjuvant / Adjuvant / Locally advanced / Metastatic
- Best response: Complete Response (CR) / Partial Response (PR) / Stable Disease (SD) / Progressive Disease (PD) / Not assessable / Unknown / Not applicable. Best response is derived from the last treatment regimen

The prior anti-cancer drugs will also be extensively detailed with the number and percentage of subjects by the drug class and PT in a table. A subject will be counted only once within a given drug class and within a given drug name, even if he/she received the same medication at different times. The summary will be sorted on decreasing frequency of drug class and decreasing frequency of drug name in a given drug class. In case of equal frequency regarding drug class (respectively drug name), alphabetical order will be used.

The following listings of prior anti-cancer treatments and procedures will also be provided: a) listing of prior anti-cancer drug therapies for non-metastatic disease, b) listing of prior anti-cancer radiotherapy and c) listing of prior anti-cancer surgeries. These will include the subject identification number, and all the relevant collected data-fields on the corresponding eCRF pages.

14 Previous or Concomitant Medications/Procedures

Analysis sets: FAS / Safety analysis set

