14.2 Subsequent Anti-Cancer Therapies/Procedures

Subsequent anti-cancer treatment will be provided in a data listing with data retrieved from “Anti-Cancer Treatment after Discontinuation Details”, “Radiotherapy after Discontinuation”, and “Surgery after Discontinuation” eCRF pages. The earliest date of start of new anti-cancer *drug* therapy will be used for the definition of the on-treatment period; the earliest date of start of any new anti-cancer therapy will be used for censoring for efficacy analyses.

15 Treatment Compliance and Exposure

Analysis sets: FAS / Safety analysis set

All dosing calculations and summaries will be based on “Avelumab Administration Details” eCRF pages.

Subjects will receive an IV infusion of avelumab at a dose of 10 mg/kg (over the duration of 1 hour [-10 minutes / +20 minutes, that is, over 50 to 80 minutes]) once every 2 weeks (one cycle). Analysis of exposure will be based on the calculated actual dose levels (total dose administered/weight, mg/kg). The last available weight of the subject within 3 days prior to the day of dosing will be used.

In case of missing total dose, the dose level as entered in the eCRF will be used.

The duration of therapy (in weeks) during the study is defined as:

$$\text{duration} = \left(\frac{\text{date of last dose} - \text{date of first dose} + 14}{7} \right)$$

The cumulative dose (mg/kg) per subject in a time period is the sum of the actual dose levels that the subject received within that period (i.e. total dose administered (mg) / weight (kg)).

Each cycle is defined by a 2-week period. The dose intensity and the relative dose intensity will be calculated for each subject across all cycles. The dose intensity (mg/kg/cycle) per cycle is defined as

$$\text{dose intensity} = \left(\frac{\text{Cumulative dose}}{(\text{duration of therapy (in weeks)})/2} \right)$$

The relative dose intensity is defined as the actual dose intensity divided by the planned dose per cycle.

The summary of treatment exposure and compliance table will include the following information:

- Duration of therapy (weeks)
- Total number of infusions received
- Cumulative dose of therapy (mg/kg)
- Dose intensity (mg/kg/cycle)
- Relative dose intensity of therapy (%)

A listing of treatment exposure and compliance will also be created to summarize the information listed above for each subject.

Partial Doses

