Appendix I Important Protocol Deviations (Identified by Medical Review or Programmed)

Inclusion and exclusion criteria are referred according to Protocol version 11.0 dated 17-May-2017

| | Category of Protocol Deviation | Description of Protocol Deviation | Deviation Code | Clinically Important | Protocol Section | Proposed check / comment |
|--|--------------------------------|--|----------------|----------------------|------------------|--------------------------|
| Inclusion criteria: | | | | | | |
| For the subject to be eligible for inclusion, each criterion must be checked 'YES': | | | | | | |
| Signed written informed consent. | Informed Consent Criteria | Subject did not meet inclusion criterion 1. | PDEV01 | | Section 5.3.1 | Medical review required |
| Male or female subjects aged >=18 years | Eligibility and Entry Criteria | Subject did not meet inclusion criterion 2. | PDEV02 | | Section 5.3.1 | Medical review required |
| Histologically proven MCC | Eligibility and Entry Criteria | Subject did not meet inclusion criterion 3. | PDEV03 | Yes | Section 5.3.1 | Medical review required |
| Subjects must not have received any prior systemic treatment for metastatic MCC. Prior chemotherapy treatment in the adjuvant setting (no clinically detectable disease; no metastatic disease) is allowable if the end of treatment occurred at least 6 months prior to study start | Eligibility and Entry Criteria | Subject did not meet inclusion criterion 3d. | PDEV18 | Yes | Section 5.3.1 | Medical review required |
| Disease must be measurable with at least 1 unidimensional measurable lesion by RECIST 1.1 (including skin lesions) | Eligibility and Entry Criteria | Subject did not meet inclusion criterion 7. | PDEV04 | Yes | Section 5.3.1 | Medical review required |
| Effective contraception for both male and female subjects if the risk of conception exists | Eligibility and Entry Criteria | Subject did not meet inclusion criterion 11. | PDEV05 | | Section 5.3.1 | Medical review required |

| | Category of Protocol Deviation | Description of Protocol Deviation | Deviation Code | Clinically Important | Protocol Section | Proposed check / comment |
|--|--------------------------------|-------------------------------------|----------------|----------------------|------------------|--------------------------|
| Exclusion criteria: | | | | | | |
| For the subject to be eligible for inclusion, each criterion must be checked 'NO': | | | | | | |

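### The Part B per-protocol criterion on prior therapy omits the word systemic, so it does not match inclusion criterion 3d or deviation PDEV18 and can be read as excluding protocol-compliant subjects

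*SAP*

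**What the plan says.** Section 10 of the Part B SAP defines the PP set as FAS subjects who meet every criterion in a list. One criterion is "No prior anti-cancer therapy for metastatic disease". Another, on CNS disease, states that "subjects with a history of treated CNS metastases (by surgery or radiation therapy) must have fully recovered from treatment", with further conditions on stability and steroids.

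The eligibility rule is narrower. Protocol Section 5.3.1, criterion 3d, bars prior systemic treatment in the metastatic setting, and allows adjuvant chemotherapy that ended at least 6 months before study start. Appendix I of the Part B SAP repeats this as PDEV18, marked clinically important: "Subjects must not have received any prior systemic treatment for metastatic MCC". Item 4 under version 3.0 in the modification history (Part B SAP, Section 4) reads "Updated Per Protocol Analysis Set definition to match current list of Clinically Important PDs".

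The PP set serves sensitivity analyses of the primary and secondary efficacy endpoints. These are skipped if PP holds at least 95% of the safety set, which in Part B is the same set as the FAS.

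**The concern.** Without the word systemic, the criterion can be taken to cover radiotherapy and surgery. A subject whose metastasis was irradiated or resected well before entry, and who had no systemic treatment for metastatic disease, satisfies 3d and commits no deviation, yet would leave the PP set. Protocol Section 8.4 describes that set as the protocol-compliant part of the treated population, and Section 9 of the Part B SAP declares no departure from the protocol's methods.

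Two things are at stake: who is in the PP set, and whether the PP analyses are run at all. Two programmers could build different sets from the same text. Protocol Section 5.1 gives Part B a confirmatory role for some approvals, so its sensitivity population should be unambiguous.

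**Working it through.** **1. The three rules side by side**

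| Source | Prior therapy barred in the metastatic setting | Adjuvant chemotherapy within 6 months |
|---|---|---|
| Protocol 5.3.1, criterion 3d | Systemic | Barred |
| Part B SAP, Appendix I, PDEV18 | Systemic | Barred |
| Part B SAP, Section 10, PP criterion | Anti-cancer therapy, type not stated | Not mentioned |

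The PP criterion differs from its counterpart twice. It may be too wide on local treatment, and it is too narrow on recent adjuvant chemotherapy, which is part of PDEV18 but does not remove a subject from PP.

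**2. What the term means in the Part B SAP.** Section 13.3.2 opens with "The prior anti-cancer therapies are collected under the" and names the drug, radiotherapy and surgery pages. Its categories include "Subjects with at least one prior anti-cancer radiotherapy". Section 14.2 uses new anti-cancer drug therapy to end the on-treatment period, but for censoring it says that "the earliest date of start of any new anti-cancer therapy will be used for censoring for efficacy analyses". So the SAP marks the narrower meaning in places where it matters.

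**3. Consistency within the PP list.** All criteria must be met. Surgery or radiation to CNS metastases is therapy for metastatic disease. On the literal reading every subject whom the CNS criterion means to keep is already excluded, so that allowance could never operate.

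**4. Is earlier local treatment a violation?** Exclusion 4 (Protocol 5.3.2) concerns "Concurrent anticancer treatment (for example, cytoreductive therapy, radiotherapy" and so on, with exceptions. Protocol 6.5.3 bars surgery to tumor lesions during treatment and in the 28 days before it. Neither bars earlier local treatment as such.

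**5. The 95% rule.** Inputs: N = 112 (Part B SAP, Section 7) and the threshold of 95% (Section 10).

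- 0.95 × 112 = 106.4, so PP must hold at least 107 subjects for the PP analyses to be skipped.
- Five exclusions: 107/112 = 95.5%, analyses skipped.
- Six exclusions: 106/112 = 94.6%, analyses run.

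The six count over all criteria together. If five subjects fail other criteria, one exclusion for local therapy tips the rule; if none do, six are needed.

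**6. The plan's precision statement.** The plan gives no figure on this point. Its general statement is that, with 112 subjects and a true durable response rate of 45%, the exact 95% lower bound exceeds 20% with probability above 99% and exceeds 30% with probability 90%. The required counts are 32 and 44 responders, and the binomial tail probabilities are 0.9999 and 0.9055, so the statement reproduces. It concerns the FAS and is untouched.

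For PP alone, take 0 to 28 exclusions as an assumed range (PP size 112 down to 84). The probability of a lower bound above 30% at a true rate of 45% would be:

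| PP size | Responders needed | Probability |
|---|---|---|
| 112 | 44 | 0.9055 |
| 106 | 42 | 0.8873 |
| 101 | 40 | 0.8833 |
| 84 | 35 | 0.7647 |

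**The case against.** The best reply is that the criterion is shorthand for systemic therapy. Several places support this:

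- Under the systemic drug heading in Section 13.3.2, the types of prior anti-cancer therapy are drug classes, without radiotherapy or surgery.
- Disease setting, including metastatic, is tabulated there only for systemic therapies.
- Item 17 of the version 3.0 history drops a listing of prior therapies for metastatic disease as not applicable to Part B, while the radiotherapy and surgery listings stay. Prior therapies there must mean drugs.
- The CNS criterion and item 4 both point to the narrower intent.

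This stands as evidence of intent: systemic was probably meant. It does not settle the operative text, because Section 13.3.2 uses the term in both senses and the PP criterion does not say which applies.

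A reader might infer that eligible subjects are certainly being dropped, or in appreciable numbers. The documents do not support that. The wording is ambiguous rather than plainly all-inclusive, and no count of subjects with only local treatment of metastases is given. Protocol Section 3.2 describes radiation and surgery as options in metastatic disease, which makes such subjects plausible but gives no frequency.

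A reader might also infer damage to the primary result. There is none: it rests on the FAS, and crossing the 95% line only adds a sensitivity analysis.

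**Conclusion.** The criterion is wrong as written and should be aligned with inclusion 3d and PDEV18. The point is minor. Sample size, the planned precision and the primary durable response rate are unaffected. The consequence is limited to PP membership and to the 95% trigger, which is reached at six exclusions of 112 from all criteria combined. The number of subjects affected cannot be derived and could be zero. That compliant subjects would leave the set depends on the literal reading. The mismatch with PDEV18, including the missing adjuvant condition, does not.

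**What to change.** Replace the criterion with: *No violation of inclusion criterion 3d (PDEV18): no prior systemic anti-cancer treatment for metastatic MCC, and any adjuvant chemotherapy ended at least 6 months before study start.*

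Inserting the word systemic alone would not be enough, because a subject with recent adjuvant chemotherapy would have a clinically important deviation and still count as per protocol. Referring to the full criterion also removes the conflict with the CNS allowance.

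The cost is one line in the SAP and a check of the PP flag in the programs, made before the database lock for the primary analysis. PDEV18 is already marked for medical review, so the information is needed anyway, and no new analysis is added.

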7.4.1.3 Definition of the Adverse Event Reporting Period

The AE reporting period for safety surveillance begins when the subject is included into the trial (date of first signature of informed consent) and continues through the trial's post-treatment safety follow-up period, defined as 10 weeks (Part A) / 90 days (Part B) after the last study drug administration.

Any SAE assessed as related to avelumab must be reported whenever it occurs, irrespective of the time elapsed since the last administration.

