All data recorded during the trial will be presented in individual data listings performed on the Safety analysis set.

Handling of missing data:

Unless otherwise specified in this SAP, all data will be evaluated as observed, and no imputation method for missing values will be used, unless otherwise specified.

In all subject data listings imputed values will be presented. In all listings imputed information will be flagged.

Missing statistics, e.g. when they cannot be calculated, should be presented as “nd”. For example, if n=1, the measure of variability (StdDev) cannot be computed and should be presented as “nd”.

Handling of incomplete dates:

Incomplete dates for disease history (initial diagnosis date, date of documented, locally advanced or metastatic disease diagnosis) will be imputed as follows:

- If the day is missing, it will be imputed to the 15th day of the month.
- If both day and month are missing and the year is prior to the year of the first study treatment, the month and day will be imputed as July 1st.
- If both day and month are missing and the year is same as the year of the first study treatment, the month and day will be imputed as January 1st.
- If the date is completely missing, no imputation will be performed.

Incomplete AE-related dates will be handled as follows:

- In case the onset date is completely missing or the onset is in the same month and year (if the day is missing) as the start of trial treatment then the onset date will be replaced by the minimum of start of trial treatment and AE resolution date.
- In all other cases the missing onset day or missing onset month will be replaced by 1.
- Incomplete stop dates will be replaced by the last day of the month (if day is missing only), if not resulting in a date later than the date of subject's death. In the latter case the date of death will be used to impute the incomplete stop date.
- In all other cases the incomplete stop date will not be imputed. If stop date of AE is after date of cut-off outcome of AE is ongoing at cut-off.
- Further information after cut-off (like fatal outcome) might be taken from Safety database and included separately into CTR.

Incomplete prior/concomitant medication dates will be imputed as follows:

- If the medication date is missing completely, then the medication date will be replaced by the start of trial treatment.

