Missing statistics, e.g. when they cannot be calculated, should be presented as 'ND' or 'NA'. For example, if N=1, the measure of variability (SD) cannot be computed and should be presented as 'ND'.

Partial dates will be imputed as follows:

Disease history

Incomplete dates for disease history (initial diagnosis date, date of documented, locally advanced, inoperable or metastatic disease diagnosis, date of response or progression in prior treatment) will be imputed as follows:

- If the day is missing, it will be imputed to the 15th day of the month.
- If both day and month are missing and the year is prior to the year of the first study treatment, the month and day will be imputed as July 1st.
- If both day and month are missing and the year is same as the year of the first study treatment, the month and day will be imputed as January 1st.
- If the date is completely missing, no imputation will be performed.

Adverse events

Incomplete AE-related dates will be imputed as follows:

- If the AE onset date is missing completely, then the onset date will be replaced by the start of study treatment.
- If only the day part of the AE onset date is missing, but the month and year are equal to the start of study treatment, then the AE onset date will be replaced by the start of study treatment. For example, if the AE onset date is --/JAN/2015, and study treatment start date is 15/JAN/2015, then the imputed AE onset date will be 15/JAN/2015.
- If both the day and month of the AE onset date are missing but the onset year is equal to the start of study treatment, then the onset date will be replaced by the start of study treatment. For example, if AE onset date is --/---/2014, and study treatment start date is 19/NOV/2014, then the imputed AE onset date will be 19/NOV/2014.
- In all other cases the missing onset day or missing onset month will be replaced by 1.

- Incomplete stop date will be replaced by the last day of the month (if day is missing only), if not resulting in a date later than the date of subject's death. In the latter case the date of death will be used to impute the incomplete stop date.
- In all other cases the incomplete stop date will not be imputed.

Prior/concomitant medication

Incomplete prior/concomitant medication dates will be imputed as follows:

- If the medication date is missing completely, then the medication date will be replaced by the start of randomized treatment.

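### Part B's adverse event onset imputation ignores the stop date, so an event with an incomplete onset that ended before first dose is counted as treatment-emergent (minor)

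*SAP*

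**What the plan says.** The Part B SAP, Section 11 (partial dates, adverse events), has three rules that end at the first-dose date:

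- Onset fully missing: "If the AE onset date is missing completely, then the onset date will be replaced by the start of study treatment".
- Day missing: "If only the day part of the AE onset date is missing, but the month and year are equal to the start of study treatment", the onset becomes the first-dose date.
- Day and month missing: "If both the day and month of the AE onset date are missing but the onset year is equal to the start of study treatment", the onset again becomes the first-dose date.

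Any other missing onset day or month is set to 1. A stop date that lacks only its day goes to the end of the month, limited by the date of death. Other incomplete stop dates are left alone. No rule compares onset with stop.

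Part B Section 17.1 makes an event treatment-emergent if its onset or worsening falls in the on-treatment period, and Section 11 starts that period at the first dose. Under Protocol Section 7.4.1.3, adverse event reporting "begins when the subject is included into the trial (date of first signature of informed consent"), and Section 7.1.1 allows screening up to 18 days before treatment.

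The Part A SAP, Section 11, handles the first two cases differently: "then the onset date will be replaced by the minimum of start of trial treatment and AE resolution date". Its year-only case falls under the default of 1.

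The Part B medication start-date rules follow the same three-case pattern, also without a stop-date check. They refer to the start of randomized treatment, which I read as the start of study treatment because the trial is not randomized.

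**The concern.** Placing an event on the first-dose date is a sensible cautious default when its timing is unknown. It is not sensible when a recorded stop date shows that the event was over before avelumab was given. The Part B rule then produces an impossible record, with onset after stop, and the treatment-emergent flag follows from that false onset.

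Such an event enters the overall treatment-emergent table and the tables by system organ class and preferred term. It enters the grade 3 or higher and serious tables if it was so recorded. It enters the related tables if the relationship was marked related or left blank, because Section 17.1 treats blank as related.

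**Working it through.** **Inputs.** The onset and stop-date rules and the start of the on-treatment period are from Part B SAP Section 11. The treatment-emergent definition is from Section 17.1. The comparison rule is the minimum in Part A SAP Section 11, extended here to the year-only case. Part B writes no formula for adverse event duration, so I assume Part A's convention (stop − start + 1) and give the result without the +1 in brackets.

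**The plan's own example.** The Part B SAP says "if the AE onset date is --/JAN/2015, and study treatment start date is 15/JAN/2015, then the imputed AE onset date will be 15/JAN/2015". Applying the rules gives the same date. Its year-only example (first dose 19 November 2014) also reproduces.

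**Test cases.** An event counts as treatment-emergent (TE) if its imputed onset is on or after first dose.

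| First dose | Recorded onset | Stop | Part B onset | TE? | Duration, days | With the minimum rule |
|---|---|---|---|---|---|---|
| 15 Jan 2015 | missing, or Jan 2015 without day | 10 Jan 2015 | 15 Jan | yes | 10 − 15 + 1 = −4 (−5) | onset 10 Jan, not TE, 1 day (0) |
| 15 Jan 2015 | Jan 2015 without day | 14 Jan 2015 | 15 Jan | yes | 14 − 15 + 1 = 0 (−1) | onset 14 Jan, not TE, 1 day (0) |
| 19 Nov 2014 | 2014 only | 5 Nov 2014 | 19 Nov | yes | 5 − 19 + 1 = −13 (−14) | onset 5 Nov, not TE, 1 day (0) |
| 10 Nov 2014 | 2014 only | Oct 2014 without day, set to 31 Oct | 10 Nov | yes | −10 + 1 = −9 (−10) | onset 31 Oct, not TE, 1 day (0) |
| 15 Jan 2015 | Jan 2015 without day | 20 Jan 2015 | 15 Jan | yes | 20 − 15 + 1 = 6 (5) | unchanged |
| 15 Jan 2015 | Jan 2015 without day | Jan 2015 without day, set to 31 Jan | 15 Jan | yes | 31 − 15 + 1 = 17 (16) | unchanged |

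The first four rows are wrong under the Part B rule and corrected by the minimum. The last two show its limits. An event that stops on or after first dose is untouched, and so is one whose stop day is missing in the month of first dose, because that stop goes to month end. The minimum therefore removes no event that the dates allow to be treatment-emergent.

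**Medications.** Part B Section 14.1 defines prior medications as those started before first dose. Concomitant ones either started earlier and continued into the on-treatment period or started during it. Take first dose on 15 January 2015, a drug start of January 2015 without day, and a stop on 10 January. The imputed start is 15 January, so the drug is not prior and becomes concomitant, although it had stopped 5 days before dosing. With the minimum, the start is 10 January and the drug is prior only.

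**The case against.** The best case against acting is that the problem is rare, visible and cautious in direction. The screening window is at most 18 days. Protocol Section 7.4.1.2 asks for complete event data, including onset and resolution dates. The analyses use cleaned data, and Part B Section 11 flags imputed values in listings. Safety analyses are descriptive, and no efficacy endpoint is touched. All of this stands and keeps the point minor. It does not make the rule right, because a flag in a listing does not change a count in a table.

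A reader might also infer more than the documents support:

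- *That every screening event with a missing onset day is affected once first dose falls on day 19 or later.* The 18-day window then lies within one month (19 − 18 = 1), so the day-missing rule applies to all such events. The error still needs a stop before first dose.
- *That Part A guards all three cases.* It guards two.
- *That Part B dropped a check it once had.* Its modification history records a different deletion from the adverse event imputation rules and says nothing of this one.
- *That negative durations will fill the tables.* Duration is specified per event only for the immune-related listing (Section 17.2.3), whose events first pass the medical review in Appendix II. A stop one day before dosing gives 0, not a negative value, under the +1 convention.
- *That screening symptoms will be tabulated as infusion reactions.* Appendix II requires occurrence during or after the infusion. Whether a false same-day onset passes depends on programming that the SAP does not give.

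**Conclusion.** The point holds as a minor error in a stated rule. In all three Part B cases, an event with an incomplete onset and a stop before first dose is counted as treatment-emergent, with onset after its own end. Nothing in Part B Sections 11 or 17.1 corrects this. The Part B SAP already recognizes the principle elsewhere, since it does not let an imputed start of subsequent anti-cancer therapy fall after that therapy's end date.

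The main effect is on treatment-emergent counts, which can only rise. The number of affected records cannot be found from the documents. I expect it to be small, because three things must coincide: an event in screening, an incomplete onset matching one of the three rules, and resolution before dosing. The treatment-emergent result does not depend on the duration convention; only the size of the impossible duration does.

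**What to change.** In each of the three Part B onset rules, replace the start of study treatment with the earlier of the start of study treatment and the adverse event stop date. Impute the stop date first, and keep the first-dose date when no usable stop date exists. Part A already states this minimum for the first two cases; the year-only case extends the same logic.

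Apply the same limit to the Part B medication start-date rules, so that a drug known to have stopped before dosing stays prior and does not become concomitant. Part A has no model for this; the reason is the pair of definitions in Part B Section 14.1.

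The cost is a few words in Section 11 and a minimum in the date-derivation code. No new data are needed, and events ending on or after first dose keep their present classification.
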